3. INVESTIGATIONAL PLAN

3.1. Study design

3.1.1. Design and methodology

This Phase IIa study aims at investigating the safety and tolerability of 2 dose-levels of ABX464 administered daily in combination with methotrexate (MTX) in patients with moderate to severe active Rheumatoid Arthritis (RA) who had an inadequate response to MTX or/and to one or more anti- tumor necrosis factor alpha (TNF α) therapies.

In addition, several experimental and clinical endpoints will be assessed to obtain information on preliminary efficacy in patients with moderate to severe active Rheumatoid Arthritis. Although no formal hypothesis will be tested, these endpoints will enable a broader understanding of the mechanism of action and potential for clinical efficacy of ABX464 in Rheumatoid Arthritis.

The first 6 patients will be randomized to receive either ABX464 50mg (n=4) or its matching placebo (n=2). The Data Safety Monitoring Board (DSMB) will review the safety of these first 6 patients dosed for at least 2 weeks. Once the DSMB recommendation is granted, the next patients will be randomized to receive either ABX464 50mg, ABX464 100mg or placebo.

Then, a second DSMB meeting will be held after the next 6 patients are randomized to check the tolerability of the 100mg dose. Once the DSMB recommendation is granted, the next patients will be randomized to receive either ABX464 50mg, ABX464 100mg or placebo.

Eligible patients will be randomized, according to a 1:1:1 ratio into 3 parallel intervention/treatment groups:

Intervention/treatment Active Arm	
Group #1 (n=20): 100mg qd	2 capsules of 50mg ABX464
Group #2 (n=20): 50mg qd	1 capsule of 50mg ABX464 + 1 capsule of matching placebo
Group #3 (n=20): Placebo	2 capsules of matching Placebo

[figure not shown]
Patients will be treated for 12 weeks, followed by a follow-up period (21 days).

The total duration of participation in the study will be approximately 15 to 19 weeks from screening to the last study visit (screening and baseline could occur at the same visit).

From Baseline / Day 0 onwards, randomized patients will be seen at the investigational site after 1 Week (Day 7), 2 weeks (Day 14), 4 weeks (Day 28), 8 weeks (Day 56) and 12 weeks (Day 84).

At Week 12 (Day 84 +/- 2 days), patients willing to carry on the study treatment will be able to take part in an open-label study (ABX464-302). In any other case, the subjects will exit the study (EOS) and will be treated according to the standard of care. The ABX464-302 follow-up study is a separate clinical study subject to health authorities and ethics committee approvals.

Study scheme:

In the present study (ABX464-301), randomization will be stratified according to a single factor: patients without previous exposure to anti-TNF α therapy versus patients with previous exposure to anti-TNF α

therapy.

3.1.2. Dose limiting toxicity (DLT)

A dose limiting toxicity (DLT) is defined as a grade 3 or higher adverse event as defined by the Common Terminology Criteria for Adverse Events (CTC-AE V5.0) considered by a safety review board as probably or definitely related to study treatment.

If more than 2 DLTs occur in the first 12 treated patients for at least 14 days, then the enrolment of additional patients in the treatment group will be stopped, otherwise the enrolment of planned patients will be confirmed.

In addition, in case of a life threatening (grade 4) adverse reaction enrolment in the treatment group, all treatment of ongoing patients will be immediately discontinued.

In both cases, enrolment will only be resumed upon the decision of the sponsor if the Data Safety Monitoring Board can conclude that the causality of the event was unrelated or unlikely related to study treatment.

3.1.3. Data Safety Monitoring Board

An independent Data Safety Monitoring Board (DSMB), with expertise and experience in the pathology, and without direct involvement in the conduct of the trial, will be set up specifically to guarantee effective protection of patients, ensure the ethical conduct of the trial, benefit/risk ratio of the trial, and to ensure the independent review of the scientific results during the trial and at the end of the trial. Besides, the DSMB may recommend the early termination of the trial at any time if an unacceptable toxicity occurs.

The DSMB will meet after the first 6 patients are dosed (50mg or matching placebo) for at least 2 weeks to check the 50mg dose tolerability. Once the DSMB recommendation is granted, the next 6 patients will be randomized to receive either ABX464 50mg, ABX464 100mg or placebo.

A second DSMB meeting will then be held when these 6 next patients are treated for at least 2 weeks, to check the 100mg dose tolerability and grant the recommendation to resume patient's randomization.

In addition, from the first DSMB onwards, meetings will be held every month during the study period. The DSMB will also review all potential causally-related Serious Adverse Events within 7 days of the initial report.

The DSMB has only a consultative role. It will inform the Sponsor who will decide whether the DSMB recommendation will be followed. A DSMB charter must be available upon submission of the trial (initial protocol) to the respective competent authorities.

3.2. Duration of study participation

Eligible patients will be enrolled in the present study at the screening visit within 30 days prior to the first dosing / randomization (screening and baseline could occur at the same visit, if all laboratory results are available).

Patients will be treated for 12 Weeks.

Patients willing to carry on the study treatment will be able to take part in an open-label study (ABX464-302). In any other case, the subjects will exit the study (End of Study Visit) and will be treated according to the standard of care. The ABX464-302 follow-up study is a separate clinical study subject to health authorities and ethics committee approvals.

The end of study (EOS) visit will be performed three weeks after the end of treatment period.

Thus, the total duration of the study participation is approximately 15 to 19 Weeks.

4. STUDY POPULATION

4.1. Number of Patients/Centers

Up to 60 patients will be randomized in this study. These patients will be enrolled in approximately 20 sites located in Europe.

4.2. Eligibility Criteria

4.2.1. Inclusion Criteria

A patient will be eligible for inclusion in this study only if ALL of the following criteria apply:

- Men or women age 18 - 75 years;
- Patient with a confirmed and documented diagnosis of adult-onset rheumatoid arthritis, for at least 12 weeks, according to the revised 2010 ACR-EULAR classification criteria, including at least one positive criteria among the following: Rheumatoid Factor (RF), Anti-Citrullinated Peptide Antibody (ACPA) or bone erosion;
- Swollen joint count of ≥ 4 (28-joint count) and tender joint count ≥ 4 (28-joint count) at screening;
- Patient with a moderate to severe disease activity score DAS28 CRP of ≥ 3.2 and CRP ≥ 5 mg/L (≥ 4.76 nmol/L) at screening;
- Patient who had an inadequate response (IR), or failed either methotrexate (MTX) or/and anti-TNF α therapy (both administered for at least 12 weeks before IR) or were intolerant to anti-TNF α therapy.

In addition, MTX treatment should be given at a stable dose ≥ 10 mg/week (for at least 4 weeks prior to randomization). The maximal dose of methotrexate should not exceed a total of 20 mg/week. MTX treatment should be associated with folic acid at a dose ≥ 5 mg/week.

For the anti-TNF α therapy, the following wash-out period will be required:

- 30 days prior to randomization for adalimumab and etanercept
- 2 months prior to randomization for infliximab, certolizumab pegol, golimumab
- Patients with the following hematological and biochemical laboratory parameters obtained within 14 days prior to baseline:
 - Hemoglobin > 9.0 g dL $^{-1}$;
 - Absolute neutrophil count ≥ 1000 mm $^{-3}$;
 - Platelets $\geq 100,000$ mm $^{-3}$;
 - Total serum creatinine ≤ 1.3 x ULN (upper limit of normal);
 - Creatinine clearance > 50 mL min $^{-1}$ by the Cockcroft-Gault equation within 60 days prior to baseline;
 - Total serum bilirubin < 1.5 x ULN;
 - Alkaline phosphatase, AST (SGOT) and ALT (SGPT) < 1.5 x ULN;
 - Negative screening for TB and HIV, HCV, HBV
- Patients are able and willing to comply with study visits and procedures as per protocol;
- Patients should understand, sign and date the written voluntary informed consent form at the screening visit prior to any protocol-specific procedures are performed;
- Patients should be affiliated to a social security regimen (for French sites only);
- Females and males receiving the study treatment and their partners must agree to use a highly effective contraceptive method during the study and for 6 months after end of study or early termination. Contraception should be in place at least 2 weeks prior to screening. Women must be surgically sterile or if of childbearing potential must use a highly effective contraceptive method. Women of childbearing potential (WOCBP) will enter the study after confirmed menstrual period and a negative pregnancy test. Highly effective methods of contraception include true abstinence, intrauterine device (IUD) or hormonal contraception aiming at inhibition of ovulation, intrauterine hormone releasing system, bilateral tubal ligation, vasectomized partner. True abstinence is defined when this is in line with the preferred and usual lifestyle of the patient. In each case of delayed menstrual period (over one month between menstruations)

confirmation of absence of pregnancy is required. This recommendation also applies to WOCBP with infrequent or irregular menstrual cycle. Female and male patients must not be planning pregnancy and male patients should use condom and must not donate sperm during the trial and for 6 months post completion of their participation in the trial.

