2.4. Secondary Endpoints

Main Efficacy Endpoint:

- Proportion of patients achieving a categorical ACR20 response at Week 12.

The components of ACR20 assessment include:

- C-Reactive Protein (CRP) (mg/L),
- Tender/painful joint count (TJC) (28 joints),
- Swollen joint count (SJC) (28 joints),
- Patient assessment of joint pain (Pain-VAS),
- Patient global assessment of disease (PtGA),
- Physician's Global Assessment of Disease (PrGA),
- HAQ-DI

Other secondary endpoints:

- Change from Baseline in the following disease parameters at Week 2, Week 4, Week 8 and Week 12:
 - Individual components of the ACR20 response (CRP, TJC(28), SJC(28), Pain-VAS, PtGA, PrGA, HAQ-DI)
 - Erythrocyte Sedimentation Rate (ESR);

- DAS28-CRP and DAS28-ESR. The components of DAS28 assessment include TJC(28), SJC(28), CRP/ESR, and PtGA;
- SDAI score which includes TJC(28), SJC(28), CRP, PtGA, and PrGA;
- CDAI score which includes TJC(28), SJC(28), PtGA, and PrGA;
- Functional Assessment of Chronic Illness Therapy (FACIT)-Fatigue score
- Proportion of patients achieving at Week 2, Week 4, Week 8 and Week 12:
 - ACR20/50/70 response
 - Categorical DAS28-CRP response. Proportion of patients achieving categorical DAS28-CRP response will be measured as moderate/good European League Against Rheumatism (EULAR) response at each assessment time point;
 - Low Disease Activity (LDA) ($\text{DAS28} \leq 3.2$)
 - DAS28-ESR remission ($\text{DAS28} < 2.6$)
 - ACR/EULAR remission (TJC(28), SJC(28), CRP, and PtGA: $\text{all} \leq 1$);
 - SDAI remission ($\text{SDAI} \leq 3.3$);
 - CDAI remission ($\text{CDAI} \leq 2.8$).
- Concentration of miR-124 expression in total blood (determined by qPCR) at baseline and week 8
- Change from Baseline in miR-124 expression in total blood at Week 8
- PK parameters:
 - Pre-dose plasma concentration of ABX464/N-Glu at Week 2 and Week 8;
 - Post-dose plasma concentration of ABX464/N-Glu at 1-, 2- and 3-hours post-dose at Baseline, Week 2 and Week 8;
 - Trough plasma concentration of ABX464/N-Glu at End of Study Visit
- The number of incidences of treatment-emergent serious adverse events;
- The number of incidences of treatment-emergent adverse events of special interest;
- The number of incidences of adverse events leading to investigational product discontinuation;
- The number of incidences of clinically significant laboratory abnormalities;
- The number of incidences of all AE (causally related and non-related) and SAE, further categorized by severity.

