5.3.5. Hematology and biochemistry

For hematology and biochemistry panels, local laboratory will be used.

Each laboratory value that is outside of the institution's normal range will be identified. The Investigator will be responsible for assessing the clinical significance of laboratory abnormalities. If the Investigator is uncertain about the clinical significance of a laboratory abnormality, he/she will consult with the Sponsor medical monitor.

The Investigator should follow any clinically significant laboratory abnormalities until resolution.

The Table 1 displays the clinical laboratory parameters that must be measured.

Table 1: Laboratory Tests

HEMATOLOGY	BIOCHEMISTRY
Hemoglobin	Sodium
Hematocrit	Potassium
WBC	Chloride
Neutrophils	Calcium
Lymphocytes	Phosphate
Monocytes	Glucose
Eosinophils	BUN or urea
Basophils	Creatinine
Platelet count	AST / SGOT
ESR	ALT / SGPT
Prothrombin time and/or INR*	Alkaline phosphatase
Fibrinogen*	GLDH
	LDH
	Lipase
	Total cholesterol
	HDL cholesterol
	LDL cholesterol
	gGT
	Total bilirubin
	Total protein
	Albumin
	CRP
	T3, T4, TSH (for French sites only)
	Troponin I & T*

Tests of TB (Quantiferon TB Gold Plus), HIV (anti-HIV Ab), HCV (anti-HCV Ab), HBV (HBsAg, anti-HBs Ab), anti-HCV Ab, will be performed only at screening. * Except at Week 1 & 2

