5.3.7. Disease parameters

• Laboratory disease parameters:

- The **acute phase reactants**, CRP and ESR, will be dosed at every visit.
- Blood samples (on gel tubes) for serum **cytokines** determination will be kept in the local laboratory, at -80°C (or -20°C if not possible), till the end of the study.
- Blood samples (on Truculture® tubes) for determination of **cytokines**, produced by immune cells after stimulation (incubation at 37°C for 24 hours), will be kept in the local laboratory, **at -20°C**, till the end of the study. These samples will be performed only where the incubation procedure is feasible.
- The blood samples for **flow cytometry cells count** (including at least B & T lymphocytes, myeloid cells and macrophages) will be kept in the local laboratory, at -80°C or will be processed immediately.

The processes for samples preparation, storage and shipment will be fully defined in the laboratory manual.

- **miR-124 modulation**

ABX464 up-regulates miR-124 in PBMCs, making this micro-RNA a potentially useful future biomarker for ABX464 treatment monitoring. Determination of miRNA level in total blood will be performed in order to assess treatment effect by comparing before and after treatment for this exploratory biomarker. Assays for miRNA determination (by qPCR method) will be conducted by a specialized central laboratory.

The total blood in Paxgene® tubes will be stored at -20°C according to lab manual instructions.

- **Disease Activity Score (DAS) 28-CRP (DAS28-CRP) and DAS28-ESR**

The components of the DAS28 include:

- tender/painful joint count (TJC) (28),
- swollen joint count (SJC) (28),
- CRP (in mg/L) or ESR (in mm/h), and
- patient global assessment of disease (PtGA), expressed as a Visual Analog Scale (VAS) from 0 to 100 mm

They are calculated with the following formula:

$$\text{DAS28-CRP} = 0.56 \sqrt{\text{TJC28}} + 0.28 \sqrt{\text{SJC28}} + 0.36 \ln [\text{CRP}(\text{mg/L}) + 1] + 0.014 \text{PtGA}(\text{VAS100mm}) + 0.96$$

$$\text{DAS28-ESR} = 0.56 \sqrt{\text{TJC28}} + 0.28 \sqrt{\text{SJC28}} + 0.70 \ln [\text{ESR}(\text{mm/h})] + 0.014 \text{PtGA}(\text{VAS100mm})$$

- **Simplified Disease Activity Index (SDAI)**

This other composite index is defined by this equation:

$$\text{SDAI} = \text{TJC28} + \text{SJC28} + \text{PtGA} + \text{PrGA} + \text{CRP}$$

- PtGA is expressed as a VAS from 0 to 10 cm,
- Investigator global assessment of disease (PrGA) is expressed as a VAS from 0 to 10 cm, and
- CRP (mg/L).

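### The CRP entry threshold is given as both 5 mg/L and 4.76 nmol/L; these are not the same level, and the nmol/L figure is about ten times too low

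*Protocol*

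**What the plan says.** Protocol 4.2.1 requires a DAS28-CRP of at least 3.2 together with "CRP ≥ 5 mg/L (≥ 4.76 nmol/L) at screening". The Protocol synopsis (Main Selection Criteria) and SAP 3.2.1 repeat the same two figures, the molar one again as "4.76 nmol/L) at screening". No section gives a molar mass or a conversion factor for CRP, and none explains the bracketed value.

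Elsewhere CRP is in mg/L. The DAS28 definition in Protocol 5.3.7 uses "CRP (in mg/L) or ESR (in mm/h), and", SDAI adds CRP in mg/L, and the ACR20 component in Protocol 2.4 is "C-Reactive Protein (CRP) (mg/L" with the same unit. CRP belongs to the biochemistry panel, for which Protocol 5.3.5 says: "For hematology and biochemistry panels, local laboratory will be used". Protocol 4.1 plans about 20 European sites.

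**The concern.** A bracketed value in a second unit should be the same threshold expressed differently. Here the molar figure looks far too small for a protein the size of CRP. A bracketed nmol/L value is useful only to a site whose laboratory reports in nmol/L, and that is where it would mislead.

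Two things are at stake.

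- **Eligibility.** Protocol 8.1.1 and SAP 6.4 class a breach of the inclusion criteria as a major deviation. Under Protocol 8.1.1 such a patient is not randomised or is discontinued, and the Per Protocol set excludes patients with major deviations. With two incompatible thresholds, the same patient is eligible or a major deviator depending on which figure is read.
- **Outcome.** CRP enters DAS28-CRP, SDAI and ACR20. A patient admitted with very low CRP has little CRP left to improve.

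**Working it through.** **Inputs.** The thresholds are 5 mg/L and 4.76 nmol/L (Protocol 4.2.1). The DAS28-CRP formula is in Protocol 5.3.7. The minimum joint counts come from Protocol 4.2.1: "Swollen joint count of ≥ 4 (28-joint count) and tender joint count ≥ 4 (28-joint count) at screening". The molar mass of CRP is an assumption: 100 to 130 kDa for the whole molecule, with 140 kDa and a single subunit of 20 to 25 kDa as wider checks.

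**Step 1: the molar mass that the plan's own pair implies.**

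M = (5 × 10⁻³ g/L) / (4.76 × 10⁻⁹ mol/L) ≈ 1,050,000 g/mol, or 1,050 kDa. This is roughly 8 to 10.5 times the assumed range.

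**Step 2: convert in both directions.**

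nmol/L = (mg/L × 10⁶) / M, with M in g/mol.

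| Assumed M (kDa) | 5 mg/L in nmol/L | Ratio to 4.76 | 4.76 nmol/L in mg/L |
|---|---|---|---|
| 100 | 50.0 | 10.5 | 0.48 |
| 105 | 47.6 | 10.0 | 0.50 |
| 115 | 43.5 | 9.1 | 0.55 |
| 125 | 40.0 | 8.4 | 0.60 |
| 130 | 38.5 | 8.1 | 0.62 |
| 140 (wider check) | 35.7 | 7.5 | 0.67 |
| 20 to 25 (subunit) | 250 to 200 | 53 to 42 | 0.10 to 0.12 |

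No row reproduces 4.76 nmol/L. Taking the subunit instead of the whole molecule widens the gap. At 105 kDa, 4.76 nmol/L is the conversion of 0.5 mg/L, not of 5 mg/L.

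**Step 3: would the other entry criteria stop a patient admitted on the nmol/L figure?**

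DAS28-CRP = 0.56√TJC28 + 0.28√SJC28 + 0.36 ln(CRP + 1) + 0.014 PtGA + 0.96

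Take the minimum joint counts, TJC28 = SJC28 = 4, so each square root is 2.

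- CRP 5 mg/L, PtGA 0: 1.12 + 0.56 + 0.645 + 0.96 = 3.29. This already meets 3.2, so for anyone with the required joint counts and CRP of at least 5 mg/L the DAS28-CRP limit adds nothing.
- CRP 0.5 mg/L, PtGA 0: 1.12 + 0.56 + 0.146 + 0.96 = 2.79. The shortfall is 3.2 − 2.786 = 0.414, which PtGA makes up at 0.414 / 0.014 ≈ 30 mm.

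A patient with CRP at one tenth of 5 mg/L, the minimum joint counts and a PtGA of about 30 mm out of 100 therefore meets the remaining activity criteria.

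**The case against.** The arithmetic is not in dispute; the case on the other side concerns consequence.

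- **No site is shown to report CRP in nmol/L.** This stands. Local laboratories at about 20 sites make unit differences possible, not established, so the effect on enrolment is conditional.
- **DAS28-CRP, in the same criterion, needs CRP in mg/L, so a site would have to convert and would then see a value below 5.** This is a real safeguard where the site does the conversion itself and compares the result with 5 mg/L. It does not settle which figure governs when the criterion offers both, and step 3 shows that the DAS28-CRP limit alone would not exclude the patient.
- **A low-CRP entrant would be visible later.** The efficacy listing is headed in mg/L, and Protocol 10.2 plans checks for out-of-range and inconsistent data. That allows detection, but perhaps only after randomisation, when the remedy is discontinuation or loss from the Per Protocol set.
- **The effect on outcomes is modest.** This also stands. CRP is one of five remaining ACR20 measures, of which three must improve, and CDAI omits it. CRP of 5 against 0.5 mg/L moves DAS28-CRP by 0.36 × (ln 6 − ln 1.5) ≈ 0.50. Such patients would be randomised like any others, so no bias between arms is shown, and the sample size and power figures are unaffected.

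**Conclusion.** The concern holds. The two thresholds differ by a factor of about 8 to 10.5 over the assumed 100 to 130 kDa, and the bracketed figure corresponds to 0.48 to 0.62 mg/L instead of 5 mg/L. The molar mass is an assumption, but the conclusion does not depend on its exact value, because agreement would need about 1,050 kDa.

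Two further readings are inferences. That 5 mg/L is the intended level rests on mg/L being the unit for every derived score. That the error is a decimal slip rests on the matching digits at 105 kDa. Whether any patient was affected depends on whether a site applied the nmol/L limit, which the documents do not show. Because this is a decision threshold for eligibility, and not background text, it should be corrected.

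**What to change.** Reconcile the two figures together in the Protocol synopsis, Protocol 4.2.1 and SAP 3.2.1. The sponsor can either replace the nmol/L value with one taken from its laboratory's stated conversion, or delete the bracket and state the criterion in mg/L only, in line with the derived scores. It should also ask the sites whether any local laboratory reports CRP in nmol/L and, if so, re-check the screening values of the patients enrolled there against the mg/L threshold before Per Protocol membership is agreed.

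The cost is one figure in three places and a short query to sites. SAP 1.1 says that recruitment was still under way when it was written, so at that point a correction could also have prevented errors in later patients.
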